1.1 Trial background and rationale

Sodium-glucose co-transporter 2 inhibitors (SGLT2i) are associated with weight loss, diverse cardiorenal benefits and improved glycaemic control. However, the effects of SGLT2i on lean (muscle) mass, physical function and fitness are uncertain. The Dapagliflozin, Exercise Training and physicAl function (DETA) trial investigates whether an SGLT2i, dapagliflozin (DAPA), alone or in combination with structured exercise training, improves physical function, fitness and strength compared to diet-induced weight loss in adults with type 2 diabetes mellitus (T2DM), overweight/obesity, and impaired physical function. The full background and trial protocol can be found in Sargeant et al. 2024 as an open access publication.

1.2 Funder

The trial is funded by AstraZeneca through an investigator-initiated grant.

1.3 Primary hypotheses

- H₀: DAPA, alone and in combination with exercise training, will not improve physical function compared with matched diet-induced weight loss.
- H₁: DAPA, alone and in combination with exercise training, will improve physical function compared with matched diet-induced weight loss, with greater improvements in the combined therapy group.

2 Methods

2.1 Trial design

The trial is a single centre parallel group randomised controlled trial, in which participants are randomised (1:1:1) to either a diet control group (DIET-CON), DAPA (10mg once daily), or DAPA with exercise training (DAPA+EX). Participants are followed up for 24 weeks, with an intermediate assessment after 12 weeks.

2.2 Randomisation

Randomisation is stratified by, sex (men/women) and ethnicity (White European/ Other) and previous use of glucose lowering therapies (mono/combination therapy).

2.3 Sample size

To detect a clinically meaningful two-unit difference in the primary outcome (mPPT), with an SD of 2.4 units, 90% power and an alpha error rate of 0.025, 38 participants per group were required to complete the trial.

2.4 Framework

This is a superiority trial. Each of the 2 intervention groups (DAPA and DAPA+EX) will be compared separately to the control group.

2.5 Interim analyses and stopping guidance

No interim analyses are scheduled.

2.6 Timing of final analysis

Analyses described in this SAP will be performed following completion of the trial and database lock.

2.7 Timing of outcome assessments

Outcomes are assessed at 24 weeks, with an intermediate assessment at 12 weeks.

3 Statistical principles

3.1 Confidence intervals and p-values

Since there are 2 primary comparisons (each intervention group vs diet control), the estimates of effect for the primary outcome will be reported with 97.5% confidence intervals. Secondary outcomes will be reported with 95% confidence intervals.

3.2 Adherence and protocol deviations

Adherence to the intervention will be summarised as follows:

DAPA+EX: Those that have complied with their study medication prescription during the intervention period (at least 75% of the prescribed medication has been taken, with no evidence to the contrary) and that adhered to at least 75% of prescribed exercise sessions.

DAPA: Those that have complied with their study medication prescription during the intervention period (at least 75% of the prescribed medication has been taken, with no evidence to the contrary).

DIET-CON: Those that achieve at least 3% weight loss or more at 24 weeks and have not initiated SGLT2i therapy through primary care during the intervention period.

Initiation of GLP-1 receptor agonist or insulin therapies in any group will also be noted.

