3.3 Analysis populations

The primary analyses will use a modified Intention-to-Treat (ITT) population, in which individuals are included in the group to which they were randomised; individuals with missing primary outcome data at follow-up will be excluded.

A sensitivity analysis of the primary outcome will be performed using two approaches: (1) Mixed Model for Repeated Measures (MMRM) incorporating both 12-week and 24-week data into the same model to account for missing data (see Section 5.2.3) and (2) a Per-Protocol (PP) population, comprising those that adhered to intervention as described above. Those that were prescribed GLP-1 receptor agonist or insulin therapies will be excluded from the PP analysis.

4 Trial population

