5.2.3 Missing data

All continuous outcomes: missing follow-up data

For all outcomes, participants with missing data will be excluded from the relevant analysis. This "complete-case analysis" is valid under the assumption that the outcome is missing at random (MAR), conditional on randomised group, baseline value and other covariates in the model.

Demographic characteristics of participants at baseline will be summarised in those with and without data for the primary outcome at 24 weeks.

Primary outcome: sensitivity analyses

A sensitivity analysis will be conducted using a mixed model for repeated measures (MMRM) to account for missing data. Under a MMRM approach, all data (e.g. at both 12 and 24 weeks) contributes to the model and missing values are implicitly handled under the assumption of MAR. For the MMRM analysis, the fixed variables of the analysis model will include randomisation group, timepoint (12 or 24 weeks), group by timepoint interaction, baseline value of the outcome, randomisation stratification variables (sex, ethnicity, background medications) and age as covariates. An unstructured covariance matrix for measurements within the same participant will be used. Post-hoc comparisons at 24 weeks will be extracted and compared to the primary analysis.

A per protocol (PP) analysis will additionally be performed, including participants who have adhered to the intervention as described in section 3.2.

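### The per-protocol rule for DIET-CON counts SGLT2i initiation as non-adherence only when it comes through primary care, so literally applied it keeps controls started by another route

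*SAP*

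**What the plan says.** Section 3.2 sets two conditions for adherence in DIET-CON. The first concerns weight: "Those that achieve at least 3% weight loss or more at 24 weeks". The second concerns the drug class under test: participants must "have not initiated SGLT2i therapy through primary care during the intervention period".

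Section 3.3 then defines "a Per-Protocol (PP) population, comprising those that adhered to intervention as described above". Section 5.2.3 restates the PP analysis as "including participants who have adhered to the intervention as described in section 3.2" and adds no condition of its own. One further exclusion appears in section 3.3: "Those that were prescribed GLP-1 receptor agonist or insulin therapies will be excluded from the PP analysis". It carries no limit on who prescribed the drug, and it does not name SGLT2 inhibitors.

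The PP analysis is one of two prespecified checks on the primary result (section 3.3: "A sensitivity analysis of the primary outcome will be performed using two approaches"). The other is the MMRM. The primary analysis itself uses the modified ITT population.

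**The concern.** For the comparison with a diet-only control, what matters is whether a control took an SGLT2i, not who started it. The rule makes the route of initiation part of the definition. A control started on the drug class by a hospital or specialist clinic therefore satisfies the SGLT2i condition as written. No other section removes that participant unless they miss the weight criterion or were prescribed a GLP-1 receptor agonist or insulin.

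The weight criterion gives little protection. Section 1.1 says that SGLT2 inhibitors are associated with weight loss, so an exposed control is, if anything, more likely to reach 3%. Section 1.1 also mentions cardiorenal benefits, and section 4.5 records cardiovascular disease at baseline, so starts outside primary care are conceivable. The SAP gives no rate for them.

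At stake is how cleanly the PP analysis compares dapagliflozin with diet-only controls. There is also a practical matter: an ambiguous membership rule would otherwise have to be interpreted after database lock, when the group data are available.

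**Working it through.** **1. The rules side by side**

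| Event in a DIET-CON participant (at least 3% weight loss reached) | Rule that applies | In the PP set as written? |
|---|---|---|
| SGLT2i started through primary care | 3.2 | No |
| SGLT2i started by another route | none | Yes |
| GLP-1 receptor agonist or insulin prescribed, any source | 3.3 | No |

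The second row is the gap. Section 5.2.3 only points back to 3.2, so it does not close it.

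**2. The plan's own planning figures**

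Section 2.3 plans for a 2-unit difference, "with an SD of 2.4 units, 90% power and an alpha error rate of 0.025", and 38 completers per group. Taking alpha as two-sided (the section does not state sidedness), the normal approximation is

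n = 2 × (z₀.₉₈₇₅ + z₀.₉₀)² × SD² / δ² = 2 × (2.2414 + 1.2816)² × 2.4² / 2² = 35.7, so 36 per group.

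With the noncentral t distribution, power is 89.97% at 37 per group and 90.8% at 38, so 38 is reproduced exactly. The point does not depend on this figure. It only supplies an effect size and a group size for the illustration.

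**3. Size of the shift (illustration only)**

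Assumptions not in the SAP:
- m controls are in the PP set, of whom k started an SGLT2i outside primary care;
- each of the k gains the full 2-unit effect, which is an upper-end value because a start part-way through the period would allow less exposure;
- the exposed controls otherwise resemble the rest.

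The control mean then rises by 2k/m, and the DAPA contrast becomes 2 × (1 − k/m).

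| k | m = 38 | Shift |
|---|---|---|
| 0 | 2.00 | 0 |
| 1 | 1.95 | 0.05 |
| 2 | 1.89 | 0.11 |
| 3 | 1.84 | 0.16 |
| 4 | 1.79 | 0.21 |

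The PP control set could well be smaller than 38, because it also requires 3% weight loss and no GLP-1 receptor agonist or insulin. If m were 20, each exposed control would move the contrast by 2/20 = 0.10, and two would give 2 × (1 − 2/20) = 1.80.

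The DAPA+EX contrast has the same control mean, so it moves by the same absolute amount. If its true effect is larger than 2 units, as section 1.3 hypothesises, the proportionate loss is smaller.

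**4. Direction**

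Write d for the true DAPA effect and e for the true DAPA+EX effect, each against diet, and let each exposed control gain d. The PP contrasts become d × (1 − k/m) and e − d × k/m. If d and e are both positive, both contrasts shrink. If d is zero, nothing moves. If d is negative and e positive, the DAPA+EX contrast grows. Movement of both contrasts toward no difference is therefore conditional on a beneficial DAPA effect.

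**The case against.** The best defence is that the phrase is shorthand. Section 2.1 gives trial dapagliflozin only to the two intervention groups, so a control can start an SGLT2i only outside the trial, and the authors may have used primary care to mean just that. The SAP nowhere says that hospital or specialist starts count as adherent. This reading is possible, but the SAP does not state it, and an analyst applying the rule as written would keep these participants. If it was shorthand, removing the qualifier changes nothing that was intended.

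The other objections limit the reach of the point, and they stand:

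- A reader might infer that the trial's main result is biased. It is not affected: the primary contrasts come from the modified ITT population, which does not use the adherence definition, and the MMRM does not use it either.
- A reader might infer that the SAP declares such controls free of SGLT2i. It says only that they adhered.
- A reader might take dilution as certain. It assumes benefit, and section 1.1 describes the effects on lean mass, function and fitness as uncertain.
- A reader might assume that such starts are common. The SAP gives no rate, and listing cardiovascular disease as a baseline descriptor does not show its prevalence. The eligibility criteria are in the published protocol, which was not available here.

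**Conclusion.** The point holds as a minor defect in the definition of an analysis set. Applied literally, section 3.2 keeps in the PP control group any participant who started an SGLT2i by a route other than primary care, if that participant also meets the weight criterion and was not prescribed a GLP-1 receptor agonist or insulin. That sits oddly beside section 3.3, which excludes two other drug classes from any source.

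The consequence is confined to the adherence summary and the PP sensitivity analysis. If DAPA is beneficial, the PP contrasts are biased toward no difference by up to about 0.05 units per such participant with 38 PP controls, and by more with fewer. This takes the full 2-unit effect in each exposed control as an upper limit. The number of such participants is unknown, and if it is small the effect is small. The documents do not support a claim that the primary conclusion is at risk.

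**What to change.** In section 3.2, delete *through primary care* from the DIET-CON criterion, so that it requires no SGLT2i initiation from any source during the intervention period. This brings it into line with the unrestricted exclusion in section 3.3; sections 3.3 and 5.2.3 then need no edit, because both refer back to 3.2. If the restriction to primary care was deliberate, the SAP should say so and give the reason. Either way, the wording should be settled before the group data are examined.

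The cost is one phrase and, possibly, a slightly smaller DIET-CON PP set. The SAP does not describe how starts outside primary care are recorded, so the trial team should confirm that the data held can identify them. The change concerns only who enters the PP set, and nothing about participants' treatment.

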3.3 Analysis populations

The primary analyses will use a modified Intention-to-Treat (ITT) population, in which individuals are included in the group to which they were randomised; individuals with missing primary outcome data at follow-up will be excluded.

A sensitivity analysis of the primary outcome will be performed using two approaches: (1) Mixed Model for Repeated Measures (MMRM) incorporating both 12-week and 24-week data into the same model to account for missing data (see Section 5.2.3) and (2) a Per-Protocol (PP) population, comprising those that adhered to intervention as described above. Those that were prescribed GLP-1 receptor agonist or insulin therapies will be excluded from the PP analysis.

4 Trial population

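### The primary mPPT analysis discards participants seen at week 12 but not week 24; the planned MMRM that would use them is only a sensitivity analysis and lacks a baseline-by-timepoint term

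*SAP*

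**What the plan says.** Sections 5.1.1 and 5.2.2 place the primary outcome at 24 weeks. Section 3.3 defines a modified ITT set in which "individuals with missing primary outcome data at follow-up will be excluded", and section 5.2.3 repeats the rule: "For all outcomes, participants with missing data will be excluded from the relevant analysis". The primary regression (5.2.2) adjusts for baseline mPPT, the stratification variables and age. It does not use the 12-week mPPT.

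Section 5.2.3 states the condition for this analysis openly: data missing at random given group, baseline and the model covariates. It then specifies an MMRM on both visits as a sensitivity analysis, with unstructured covariance. The fixed effects begin "randomisation group, timepoint (12 or 24 weeks), group by timepoint interaction, baseline value of the outcome" and continue with the stratification variables and age. No baseline-by-timepoint term is listed. The 24-week contrasts from this model are to be set against the primary result.

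The trial is sized on completers: "38 participants per group were required to complete the trial" (section 2.3).

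**The concern.** Two things are at stake.

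**Assumption and data used.** The 12-week mPPT is the latest earlier reading of the primary outcome, and it is outside the set on which the complete-case analysis conditions. If participants doing poorly at week 12 tend to leave, and do so more in one arm, the completers' contrast is distorted. The arms differ in kind: diet, a daily drug, or the drug plus prescribed exercise sessions. Section 5.3 lists musculoskeletal injury as an event of interest for exercise, which could both lower mPPT and lead to withdrawal. Arm-specific drop-out is therefore possible, though nothing in the SAP shows that it occurs. The primary p-value also opens the DAPA versus DAPA+EX comparison in section 5.2.7, so a bias would carry forward.

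**Meaning of the planned comparison.** The MMRM is meant to show whether missing data affect the result. With one baseline slope forced on both visits, it can differ from the 24-week regression even when nothing is missing, so a gap between the two cannot be put down to missing data.

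**Working it through.** **1. The SAP's own figure.** Inputs from section 2.3: difference 2, SD 2.4, power 90%, alpha 0.025 (taken as two-sided, in line with the 97.5% intervals).

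n = 2(z₀.₉₈₇₅ + z₀.₉₀)²(SD/difference)² = 2 × (2.2414 + 1.2816)² × (2.4/2)² = 35.7, so 36 per group by the normal approximation. The exact t test gives power 0.8997 at 37 and 0.908 at 38. The stated 38 is reproduced.

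**2. Precision under random drop-out.** Let d be the fraction missing at week 24, all of them seen at week 12, and r the 12/24-week correlation given baseline. The likelihood estimate of a 24-week mean has variance proportional to (1 − r²)/n₂₄ + r²/n₁₂; the complete-case mean has 1/n₂₄. With n₂₄ = (1 − d)n₁₂ the ratio is 1/(1 − r²d).

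- r = 0.7, d = 0.14: 1/(1 − 0.0686) = 1.07
- r = 0.7, d = 0.17: 1/(1 − 0.0833) = 1.09
- Corners of the assumed range: 1.06 (r = 0.6, d = 0.15) and 1.11 (r = 0.7, d = 0.20)

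In terms of sample size: with 38 completers of 48 randomised per arm and r = 0.6, the variance term is 0.64/38 + 0.36/48 = 0.02434, an effective 41.1 per arm. Normal-approximation power goes from 0.918 to 0.938.

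**3. Bias in the 24-week contrast.** Drop-out mechanism, rate and correlation are assumptions; the SAP gives none. A two-arm simulation used 48 per arm, true effect 2.0, SD 2.4, r = 0.6, about 18-22% drop-out after week 12, baseline as the only covariate and 400 runs. Monte Carlo error is about 0.54/√400 = 0.03.

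| Baseline slope at weeks 12, 24 | Drop-out and 12-week mPPT | Complete case | MMRM as written | MMRM + baseline × time |
|---|---|---|---|---|
| 0.7, 0.7 | unrelated | 2.04 | 2.03 | 2.03 |
| 0.7, 0.7 | related, alike in both arms | 1.94 | 1.99 | 1.98 |
| 0.7, 0.7 | related, active arm only | 2.21 | 2.01 | 2.02 |
| 0.7, 0.7 | related, opposite directions | 2.42 | 2.00 | 2.00 |
| 0.8, 0.5 | related, alike in both arms | 1.93 | 1.98 | 1.97 |
| 0.8, 0.5 | related, active arm only | 2.18 | 1.94 | 1.99 |
| 0.8, 0.5 | related, opposite directions | 2.37 | 1.82 | 1.94 |

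Simulations with r = 0.7 agree. Drop-out alike in both arms gave complete-case means of 1.95 to 2.01. Drop-out in the active arm only gave 2.21 to 2.30, against 2.00 to 2.01 for the likelihood model.

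**4. Drop-outs who leave before week 12.** With half of the drop-outs gone before the week-12 visit, the likelihood estimate is biased too: 2.14-2.15 (complete case 2.30) in the active-arm-only case, and 2.24 (complete case 2.54) with opposite patterns.

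**5. No missing data.** With 38 per arm, slopes 0.8 and 0.5 and 100 runs, the MMRM as written differed from the 24-week regression by up to 0.21 units (SD of the difference 0.08). With baseline × time added, the two agreed to rounding (3 × 10⁻¹⁴). This exact agreement is for baseline as the only covariate. In the SAP's model, sex, ethnicity, medication and age would still have one coefficient for both visits, so a residual difference could remain.

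**The case against.** The case for leaving the plan alone is substantial. The SAP states its assumption, pre-specifies the MMRM, reports completeness by arm and visit (section 4.4), and compares the baseline profile of those with and without 24-week data. Which of two pre-specified models carries the primary label is a design choice, and the SAP does not contradict itself. All of this stands, and it limits the severity.

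Four stronger readings are tempting, and the document supports none of them:

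- **The primary estimate is biased unless drop-out is unrelated to week 12.** This is too strong for a contrast between arms. When the relation is alike in both arms, the shift is close to zero and towards the null.
- **The effect may be inflated by about a quarter.** An estimate of 2.48 against 2.00 (+24%) does arise, but only with opposite drop-out mechanisms in the two arms. Nothing in the SAP points to that.
- **The trial loses planned power.** It does not. The 38 per group are completers, which matches a completer analysis; the precision is a gain forgone.
- **The MMRM cures the problem.** Its near-exact recovery in the table follows from assuming that every drop-out was seen at week 12. Step 4 shows that it is better than complete case but still biased otherwise. Neither model covers data missing not at random.

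It is also fair to say that the missing interaction is a modest specification point. An SD of 0.08 is 4% of the two-unit target, and when the true slopes are equal the average estimates with and without the term agree within 0.01. By itself it would not justify changing the primary analysis.

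**Conclusion.** The point holds as a conditional weakness that is cheap to mend. The primary analysis sets aside outcome data that the trial collects, and it rests on a stronger missing-data assumption than a model already in the SAP. Under the assumptions given (about 15-20% missing at week 24, correlation 0.6-0.7, true effect 2), the active-arm-only bias of +0.2 to +0.3 is 10-15% of the two-unit target. It is about 0 to -0.06 units if drop-out works alike in both arms (the 1.93 in the table is within simulation error of that), and it exceeds +0.3 only with opposite patterns.

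The missing baseline-by-timepoint term matters whatever the drop-out pattern, because it blurs the one comparison meant to reveal a missing-data effect.

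A reader might go on to infer that every secondary outcome measured at both visits needs the same model. The argument here concerns the primary outcome only and does not establish that.

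**What to change.** - In section 5.2.3, add a baseline mPPT-by-timepoint interaction to the MMRM. This is the minimum change and is worth making even if the primary analysis stays as it is.
- In sections 3.3 and 5.2.2, make the 24-week contrasts from that model the primary analysis, with 97.5% confidence intervals, in all randomised participants with a 12- or 24-week mPPT.
- Keep the complete-case regression as the supportive analysis.
- Record the change in section 5.2.1 as a deviation from the published plan, before any unblinded analysis.

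The cost is SAP wording, a slightly more complex primary model and a documented change of primary analysis. How far it departs from the published plan cannot be judged here, because that plan is not at hand. The sample size is unaffected.

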4.1 Screening data

No screening data were collected.

4.2 Eligibility criteria

Eligibility criteria are described in Sargeant et al. 2024.

4.3 Recruitment

The numbers of individuals invited and recruited will be reported in the CONSORT diagram.

4.4 Withdrawal/loss to follow-up

The number (%) of individuals with complete data for the primary outcome (mPPT) and all specified secondary outcomes at baseline, 12 and 24 weeks will be reported by randomised group.

4.5 Baseline demographic characteristics

The following baseline characteristics will be summarised by randomised group, using mean and standard deviation (SD) for continuous variables with reasonably symmetric distributions, median and interquartile range (IQR) for continuous variables with skewed distributions, and number and percentage for binary or categorical variables.

- Age (yrs).
- Sex (men, women).
- Ethnicity (White European, South Asian, Other).
- Cardiovascular disease (myocardial infarction, angina, other).
- Hypertension (yes, no, unknown).
- Hypercholesterolemia (yes, no, unknown).
- Medication type (glucose lowering, antihypertensive, lipid lowering).
- Social deprivation (IMD score).
- Smoking status (current, past, never).
- Alcohol status (current drinker, ex-drinker, never) and alcohol consumption (units).
- Employment type (employed [full or part time], unemployed, retired, other).

Baseline values of all outcome variables will be summarised alongside the results at 12 and 24 weeks, as described in section 5.2.2.

5 Analysis

